## 1. Purpose

To study the impact of different incentive structures and weight management practices (i.e. self-weighing, weight goal setting, exercise goal setting) on gestational weight gain management.

## 2. Rationale

Gestational weight gain (GWG) is a serious public health concern, and 37% of normal weight, 64% of overweight, and 49-64% of obese women exceed the Institute of Medicine's GWG guidelines. Research has found that modest financial incentives are a promising pragmatic strategy for a GWG intervention. Yet, most previous weight management research that has utilized incentives has targeted weight outcomes rather than the behaviors necessary to achieve them. This study to examine the impact of frequent chances to win small, proximal incentives for meeting short-term goals of monthly self-weighing and larger incentives for meeting overall GWG goals by the end of the 36-week gestational period.

## 3. Study/Project Population

There will be 50 mother and baby pairs (N=100) included to account for screening failures but only 40 of those pairs (N=80) randomize. Pregnant participants (N=100) in their first trimester at an OB-GYN Specialists clinic in Memphis, TN will be randomized in a fractional factorial experiment. Participants must be at least 18 years old and be less than 12 weeks gestation upon recruitment (based on the date of their last menstrual period and then confirmed by their physician at their first prenatal visit), as interventions that begin prior to gestational week 12 are more effective.

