their eligibility (i.e. whether participants are 18 years or older, whether they are no more than 12 weeks pregnant, and whether they have wireless internet or a Bluetooth connected device). Eligible participants will first answer a few questions about the number of pregnancies they have prior to the current one, age, annual household income, marital status, employment status, household size, education level, race, and ethnicity. Then, they will be randomized to one of the study arms and led through an automated description of the details specific to that arm. Participants will be provided with details regarding how to contact the research team via email or phone at any time if they subsequently wish to withdraw from the study. This contact information will remain easily accessible via the participants' individual Way to Health web portal dashboards throughout the study.

Participants (N = 40) will be randomized to one of 8 conditions , with combinations of 3 different components of incentive for GWG management and physical activity. Assessments will be conducted at baseline (i.e., in the first trimester), 32 weeks gestation and 36 weeks gestation (if the participant has not yet delivered) and will include measures of body weight and treatment satisfaction. Participants will be asked to complete daily weigh-ins using the scale provided by the study, as well as wear a physical activity tracker (i.e. Fitbit).

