#### Monthly GWG component

Participants randomized to an arm that contains the monthly GWG incentive component will receive \$14 per month if they have gained within the recommended monthly range for their BMI category (Table 2). "Ineligible for incentive" participants will be specifically notified that

they would have received \$14 had they had gained within the recommended range for the month, drawing on research showing that loss aversion can be motivating. Participants will receive their monthly balance on the first weekday of the following month. A maximum of \$112 could be earned over the pregnancy.

Table 2. Monthly weight gain goals by weight status

		Monthly Weight Gain Goals		
		Normal Weight	Overweight	Obese
1st Trimester	Week 5-8	< 2.2 lbs	< 2.2 lbs	< 2.2 lbs
	Week 9-12	< 2.2 lbs	< 2.2 lbs	< 2.2 lbs
2nd Trimester	Week 13-16	2 - 4.4 lbs	1 - 3 lbs	1 - 2.2 lbs
	Week 17-20	2 - 4.4 lbs	1 - 3 lbs	1 - 2.2 lbs
	Week 21-24	2 - 4.4 lbs	1 - 3 lbs	1 - 2.2 lbs
3rd Trimester	Week 25-28	2 - 4.4 lbs	1 - 3 lbs	1 - 2.2 lbs
	Week 29-32	2 - 4.4 lbs	1 - 3 lbs	1 - 2.2 lbs
	Week 33-36	2 - 4.4 lbs	1 - 3 lbs	1 - 2.2 lbs

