## 5. Study/Project Procedures

- a. recruitment
- b. randomization into study arms
- c. participants receive feedback about whether their numbers were drawn in the lottery and whether they won the incentive pending weight management results
- d. study team analyzes whether different incentive structure affects participants' gestational weight gain

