## 6. Outcome Measures

**Intervention Satisfaction:** At 32 weeks gestation, participants will be asked to offer insight into program acceptability in each condition, as well as satisfaction to the program in general. We will examine feedback on specific intervention aspects, which will inform program refinement and future implementation.

**Recruitment yields observed from enrollment survey:** The number of participants initially recruited for the study will be closely monitored.

**Program retention observed from enrollment and follow-up surveys:** The number of participants stayed in the study within the time frame of the study will be closely monitored.

**Gestational Weight Gain** (i.e., baseline to final prenatal visit): At all measurement visits, weight will be recorded in kilograms on a calibrated research-grade scale. Weight will be measured on a calibrated digital scale in duplicate, with the participant wearing light clothing and no shoes. While we will obtain the mother's weight at baseline, we will also obtain self-reported preconception weight (before the last menstrual period). We will calculate the participant's GWG goal based on self-reported preconception BMI. Strong concordance between self-reported preconception weight and measured pregravid weight has been demonstrated. The difficulty of anticipating when a final weight should be obtained to capture the fullest extent of GWG was considered, and we elected to use an approach that afforded two possible weights that would be available for analytic purposes. The Week 36 weight will be the primary outcome except for mothers who deliver prior to 36 weeks, in which case we will use the Week 32 weight. Thus, we will have a final observation of GWG for all participants, regardless of whether they deliver earlier than 36 weeks. However, only approximately 11% of pregnant women have their child before 37 weeks; thus, we expect that we will be able to collect Week 36 data on most participants.

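### The population section says 100 pregnant participants are randomised when the plan's own counts give 40; separately, and minor, the promised comparison of incentive structures has no stated method

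*Combined protocol and SAP*

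**What the plan says.** On the sample size, section 3 (Study/Project Population) has two consecutive sentences. The first reads: "There will be 50 mother and baby pairs (N=100) included to account for screening failures but only 40 of those pairs (N=80) randomize". The second reads: "Pregnant participants (N=100) in their first trimester at an OB-GYN Specialists clinic in Memphis, TN will be randomized in a fractional factorial experiment". Section 4 (Research Design) gives a third statement: "Participants (N = 40) will be randomized to one of 8 conditions".

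On the comparison, section 1 gives the purpose as "To study the impact of different incentive structures and weight management practices", and section 2 says "This study to examine the impact of frequent chances to win small, proximal incentives". Item d of section 5 (Study/Project Procedures) says that the "study team analyzes whether different incentive structure affects" participants' GWG. The Analysis Plan calls the trial a feasibility study, makes piloting the intervention components an additional aim, and states that the trial was not powered for differences in treatment engagement or GWG. The methods it names are counts, percentages, means and SDs, applied to the characteristics of the sample, together with the software.

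**The concern.** The number randomised is a figure the trial relies on. Recruitment, randomisation and retention are part of its stated primary purpose, and each is read against that number. Two consecutive sentences give incompatible values. A reader who took 100 at face value would expect 12.5 women per condition instead of 5, and intervals narrower by a factor of sqrt(100/40) = 1.58 than 40 women can give.

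The second matter is one of alignment. One section says that the effect of incentive structure on GWG will be analysed; the section that should say how does not mention it. With 8 conditions there are several ways to summarise GWG and engagement, and the text does not say which will be reported.

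**Working it through.** **Inputs.** Included: 50 pairs. Randomised: 40 pairs (both from the first sentence of section 3). Randomised participants: 40, to 8 conditions (section 4). Each pair is one pregnant woman and one baby.

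**Reproducing the plan's counts.**
- Included head count: 50 x 2 = 100. This matches the N attached to the 50 pairs.
- Randomised head count: 40 x 2 = 80. This matches the N attached to the 40 pairs.
- Allowance for screening failures: 50 - 40 = 10 pairs, and 10/50 = 20%. The rate is implied, not stated.

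**Testing the disputed sentence.**
- Pregnant women included: 50 x 1 = 50. Randomising 100 would need 100/50 = 200% of the women available.
- Pregnant women randomised: 40 x 1 = 40. This matches section 4.
- Ratio of stated to derived: 100/40 = 2.5.
- Per condition: 40/8 = 5, a whole number; 100/8 = 12.5, which is not.

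The 100 therefore matches only mothers plus babies among the included pairs. The likeliest explanation is that this head count was carried over into a sentence about pregnant women randomised.

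**Setting section 5 against the Analysis Plan.** Item d of section 5 names an outcome (GWG) and an exposure (incentive structure). The Analysis Plan's descriptive methods are tied to sample characteristics. It gives no summary by component or by condition, and no estimate or interval, for GWG or for the two engagement measures (daily self-weighing and weekly active minutes).

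**What exploratory estimates could deliver.** The documents give no SD, so results are in outcome-SD units. Assumption: the 8 conditions are a balanced 2x2x2 with 5 women each and complete data.
- Component main effect, 20 v 20: SE = sqrt(2/20) = 0.316. A main-effects model leaves 40 - 4 = 36 degrees of freedom, t = 2.03, so the 95% half-width is 0.316 x 2.03 = 0.64.
- One condition against another, 5 v 5: SE = sqrt(2/5) = 0.632. With 40 - 8 = 32 degrees of freedom, t = 2.04, so the half-width is 0.632 x 2.04 = 1.29.

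Under that assumption a component estimate is about twice as precise as a comparison of two single conditions, and still wide.

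**The case against.** The strongest reply is that the 100 is an editorial slip. The sentence before it and section 4 both give the right number, and with 50 women included nobody could set up a randomisation of 100. That stands, and it limits the severity. It does not make the sentence correct.

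On the comparison, the reply is that an unpowered feasibility study needs no efficacy analysis, and that section 6 already fixes the GWG time point (week 36, or week 32 after an earlier delivery). This largely stands. It excuses the absence of a powered test, and it removes one source of choice after the data are seen. It does not supply a method for what item d of section 5 says will be done.

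Two stronger readings are tempting and are not supported:

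- **Retention denominator.** Section 6 lists "Program retention observed from enrollment and follow-up surveys" and describes it as a number, so a reader might infer that retention could be reported out of either 50 or 40. But section 4 places the eligibility questionnaire before randomisation, and the follow-up visits come after it. Women who fail screening have no follow-up in which to be retained. The natural denominator is the 40 randomised women; leaving it unstated is missing detail, not an error.
- **The design label.** Eight conditions from three components might suggest a full factorial, so that fractional looks wrong. The list of conditions is not visible in the text available here. The first visible table caption is "Table 2. Monthly weight gain goals by weight status", so an earlier table may have been lost when the document was converted. No error in the design can be inferred from that.

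**Conclusion.** The sentence in section 3 is wrong as written. The plan randomises 40 pregnant women, an average of 5 in each of 8 conditions, not 100. This follows from the plan's own counts and needs no outside assumption.

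The mismatch between section 5 and the Analysis Plan is real but secondary. The documents plan no hypothesis test and claim no power for GWG, so this is not evidence of an underpowered efficacy trial or of an intention to choose contrasts after seeing the data. The 0.64 SD half-width rests on the assumed balanced 2x2x2 and complete data; it indicates what an exploratory estimate would offer and is not a deficiency in the plan.

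Overall severity: minor.

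**What to change.** 1. Section 3: correct the sentence so that it agrees with section 4, for example: 50 mother-baby pairs will be included to allow for screening failures; 40 pregnant participants will be randomised. Cost: one sentence.

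2. Align item d of section 5 with the Analysis Plan in one of two ways:
   - Add to the Analysis Plan exploratory component-level estimates with 95% confidence intervals, and no significance claims, for GWG, self-weighing days and active minutes. Cost: one simple model per outcome in R. Downside: the estimates are imprecise (about 0.64 SD either way under the assumption above), and a main effect averages over the other components.
   - Or reword item d as a descriptive summary of GWG. Cost: one bullet. Downside: the impact wording in sections 1 and 2 then has only a descriptive summary behind it.

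Neither route needs extra participants or data.

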## 4. Research Design

Potential participants will be identified by the clinics' health professionals (i.e., nurses, obstetricians) at their pregnancy confirmation visit or will be self-identified through recruitment materials posted in the obstetric clinic (e.g., exam rooms, lobby and bathrooms). They will be encouraged to contact the study team if they wish to learn more about the study and potentially enroll in the study. Interested individuals will be evaluated for the eligibility criteria (see above) and written informed consent will be obtained.

Upon recruitment, individuals who are interested in learning more about the study will be directed to the Way to Health web portal. Upon reaching the portal, potential participants will be asked to create an account and will then be informed of the details of the study, including its objectives, duration, requirements, and financial payments. If participants are still interested in participating, the Way to Health portal will take them through an automated online informed consent. The consent document will be divided into sections and potential participants will have to click a button to advance through each section. This is to help ensure that participants read the consent form thoroughly by breaking down the form into manageable blocks of text. Successive screens will explain the voluntary nature of the study, the risks and benefits of participation, alternatives to participation, and that participants can withdraw from the study at any time. On the final consent screen, potential participants who click a clearly delineated button stating that they agree to participate in the study will be considered to have consented to enroll. After consenting, participants will complete an online questionnaire to determine

their eligibility (i.e. whether participants are 18 years or older, whether they are no more than 12 weeks pregnant, and whether they have wireless internet or a Bluetooth connected device). Eligible participants will first answer a few questions about the number of pregnancies they have prior to the current one, age, annual household income, marital status, employment status, household size, education level, race, and ethnicity. Then, they will be randomized to one of the study arms and led through an automated description of the details specific to that arm. Participants will be provided with details regarding how to contact the research team via email or phone at any time if they subsequently wish to withdraw from the study. This contact information will remain easily accessible via the participants' individual Way to Health web portal dashboards throughout the study.

Participants (N = 40) will be randomized to one of 8 conditions , with combinations of 3 different components of incentive for GWG management and physical activity. Assessments will be conducted at baseline (i.e., in the first trimester), 32 weeks gestation and 36 weeks gestation (if the participant has not yet delivered) and will include measures of body weight and treatment satisfaction. Participants will be asked to complete daily weigh-ins using the scale provided by the study, as well as wear a physical activity tracker (i.e. Fitbit).

#### Self-Weighing (Lottery)

Participants randomized to an arm that contains the self-weighing (lottery) component will be asked to pick a number between 00 and 99 at randomization, and will be informed that there will be a daily lottery, for which they will be eligible if they have weighed themselves in the previous day on the Withings e-scale. Then, for each day of their pregnancy, participants will be informed of the study's randomly-generated winning lottery number. Participants who weighed themselves the previous day with a one- or two-digit match will be also specifically notified of their reward. A two-digit match (1 in 100 chance) will yield a \$15 incentive and a single-digit match (1 in 5 chance; that is, if the participant's lottery number is 27, an example of a one-digit match is 77) will yield a \$2 incentive. A maximum of \$112 could be earned over the pregnancy. Participants will receive their weekly winnings from weigh-in on Mondays of the following week.

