#### Self-Weighing (Certain Loss)

Participants randomized to an arm that contains the self-weighing (certain loss) component will have a balance shown at the beginning of the study on the participant dashboard and each day that they do not weigh, \$0.50 will be subtracted from this account. The beginning balance will be based on the number of days until 36 weeks gestation for each participant, which will vary slightly due to when participants enroll in the study. Participants will receive their weekly payout (a maximum of \$3.50 for 7 days) from weigh-in on Mondays of the following week. A maximum of \$112 could be earned over the pregnancy.

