## *Other Measures*

**Height:** Height will be recorded in centimeters.

**Demographics:** Participants will complete a questionnaire regarding their age, annual household income, marital status, employment status, education level, race, and ethnicity.

**Weight Self-Monitoring:** We will electronically monitor daily self-weighing as a measure of treatment engagement (coded each day as present or absent).

**Physical Activity:** We will electronically monitor participants' weekly physical activity as a measure of treatment engagement (measured in active minutes).

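### The lottery's stated 1 in 5 chance of a single-digit match should be 18 in 100, the matching rule is not defined, and only the lottery component describes a daily notice

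*Combined protocol and SAP*

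**What the plan says.** All of this is in Section 4 (Research Design) of the combined protocol and SAP unless noted.

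- **Lottery rules.** Under Self-Weighing (Lottery), each participant "will be asked to pick a number between 00 and 99 at randomization". There is a daily draw, "for which they will be eligible if they have weighed themselves in the previous day on the Withings e-scale".
- **Lottery prizes.** "A two-digit match (1 in 100 chance) will yield a \$15 incentive". The smaller prize, $2, goes to "a single-digit match (1 in 5 chance; that is, if the participant's lottery number is 27, an example of a one-digit match is 77". The maximum over the pregnancy is given as $112.
- **Lottery notices.** The plan says that "for each day of their pregnancy, participants will be informed of the study's randomly-generated winning lottery number". Those who weighed and matched are told of their reward as well. No channel is named.
- **Certain loss.** Under Self-Weighing (Certain Loss), participants "will have a balance shown at the beginning of the study on the participant dashboard and each day that they do not weigh", $0.50 is deducted. The starting balance depends on the days left to 36 weeks. Payout is on Mondays, at most $3.50 a week, again with a $112 maximum. The text neither describes nor excludes a daily notice.
- **Outcome affected.** Under Other Measures: "We will electronically monitor daily self-weighing as a measure of treatment engagement (coded each day as present or absent".
- **Status of comparisons.** The Analysis Plan calls this a feasibility study that also pilots the components. It is not powered to compare conditions on engagement or weight gain, and the analyses described are descriptive.

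**The concern.** The odds and the matching rule together fix what the lottery is worth. They have to be programmed into the draw, and they are likely to reach participants, because Section 4 says that each woman is led through an automated description of her own arm. Odds that do not follow from the rule mean that women may be told something slightly untrue. A rule with two readings means that the programmer decides what the incentive is. Under one reading, a woman's chance of winning would depend on a number she chose without knowing that it mattered.

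The secondary matter concerns interpretation. A daily announcement linked to the scale can act as a reminder to weigh, and daily weighing is the engagement measure. If one component carries such a notice and the other does not, a descriptive contrast between them could mix how often women are contacted with the type of incentive they are offered.

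**Working it through.** **Inputs.** From Self-Weighing (Lottery): 100 equally likely numbers, $15 for two digits, $2 for one digit, stated single-digit odds of 1 in 5, maximum $112. From Self-Weighing (Certain Loss): $0.50 per day, maximum $112.

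**1. The plan's own figure.** Adding the chance for each digit gives 0.1 + 0.1 = 0.20, or 1 in 5. This counts the two-digit match twice.

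**2. Same-position matching.**
- Exactly one digit: 2 x 0.1 x 0.9 = 0.18, about 1 in 5.6.
- At least one digit, with the two-digit match included: 1 - 0.9 x 0.9 = 0.19.

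Neither equals 0.20. Because the two-digit match has its own prize, 0.18 is the figure that applies. Listing all 100 draws gives 18 for every number checked (27, 77, 00 and 05).

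**3. Any-position matching.** The example of 27 against 77 shares the 7 in the second place, so it satisfies both rules and does not decide between them.
- Pick 27: draws containing a 2 or a 7 number 100 - 8 x 8 = 36; less 27 itself, 35.
- Pick 77: draws containing a 7 number 100 - 9 x 9 = 19; less 77 itself, 18.

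**4. Value per weigh-in day, before any cap.** Value = 0.01 x 15 + p x 2.

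| Rule | p | Lottery value | Ratio to $0.50 |
|---|---|---|---|
| Same position, exact | 0.18 | 0.15 + 0.36 = $0.51 | 1.02 |
| As stated | 0.20 | 0.15 + 0.40 = $0.55 | 1.10 |
| Any position, two different digits | 0.35 | 0.15 + 0.70 = $0.85 | 1.70 |

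Correcting the stated odds therefore brings the lottery closer to certain loss.

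**5. The $112 maximum.** For certain loss it is a true ceiling: 224 days x $0.50 = $112, which is 32 weeks. For the lottery, nothing in the prize rule stops winnings at $112. The expected total over 224 days is 224 x 0.51 = $114.24, so $112 looks more like an expected total unless it is enforced. The table gives the effect of enforcing it, from the exact distribution of summed winnings at p = 0.18, for a woman who weighs every day. The follow-up lengths are assumptions: 168 days is entry at week 12, 182 days entry at week 10, and 224 days entry at week 4.

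| Days | Lottery, no cap | Lottery, capped | Capped, per day | Certain loss | Chance that uncapped winnings exceed $112 |
|---|---|---|---|---|---|
| 168 | $85.68 | $84.15 | $0.50 | $84.00 | 11% |
| 182 | $92.82 | $90.02 | $0.49 | $91.00 | 18% |
| 224 | $114.24 | $103.34 | $0.46 | $112.00 | 50% |

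**6. Notices.** With entry at week 10 (assumed), the lottery text implies 26 x 7 = 182 daily announcements to week 36. Both components also have about 26 Monday payouts. No daily notice is described for certain loss. The monthly weight-gain and physical-activity components do state when participants are notified, so notification is normally written down component by component.

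**The case against.** **The odds slip is small.** One in 5 against 1 in 5.6 looks like simple rounding or double counting. This stands as to size. It is still a stated parameter of the intervention that does not follow from its own rule, and correcting it costs almost nothing.

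**The any-position reading is unlikely.** For 27, the plan's own example, it gives 35 in 100, which cannot be squared with a stated 1 in 5; same-position matching comes close. This stands: same position is very probably what was meant. A reader might infer from the 1.70 ratio that the lottery pays 70% more, but that rests on a rule which the plan's own odds contradict, and it ignores the $112 maximum. If $112 is enforced, lottery winnings over 182 days cannot exceed 112 / 91 = 1.23 times the certain-loss total. The ambiguity is a reason to write the rule down and does not show an imbalance.

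**Silence about notices does not mean there are none.** A reader might infer that certain-loss women get only a dashboard balance. The plan does not say so. It also names no channel for the lottery notice, which could itself appear on the dashboard. What remains is that one component describes a daily notice and the other does not.

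**No inference is at risk.** The pilot is unpowered, specifies no test of lottery against certain loss, and gives no rule for choosing between them. Announcing the draw is also part of how a daily lottery works, so comparing the components as packages is legitimate. This largely stands and makes the notice point secondary. Lack of power does not remove the mixing from a descriptive comparison, but careful wording deals with it.

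**Conclusion.** The point holds for the odds and the matching rule. The stated 20 in 100 should be 18 in 100, assuming equally likely draws, same-position matching and separate payment of the two-digit match. As worded, the rule also admits a reading under which the odds vary with the number picked, from 18 to 35 in 100 in the two examples.

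It might be inferred that the error makes the two self-weighing incentives unequal in daily value. The documents do not support that: at the correct odds the difference is $0.01 per weigh-in day, or 2%, before any cap. The undefined status of the $112 maximum matters more for women who enter early. If it is enforced, the lottery averages about $0.46 per day over 224 days against $0.50, with almost no difference over 168 days, assuming weighing every day.

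The difference in described notices is a fair reading of the text and a secondary point. It limits what a contrast in daily weighing could be said to show, in a pilot that does not formally plan that contrast.

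**What to change.** 1. In Self-Weighing (Lottery), and in the arm description shown to participants, define a one-digit match as the same digit in the same position with the other digit different, and replace 1 in 5 with 18 in 100. Check that the programmed draw follows this rule. The cost is a wording correction; the odds quoted to participants become slightly less favourable.
2. In the same section, state whether $112 is an enforced cap on lottery winnings or an approximate expected total. This costs one sentence.
3. Secondary: state the notice schedule and channel for both self-weighing components. Then either match frequency and channel, which costs one automated message template and adds messages to the certain-loss component, or leave the components as they are and say in the Analysis Plan that any difference in daily weighing will be described as one between incentive packages, not incentive type alone. The second option costs one sentence and leaves the interventions unchanged.
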